10.2.4.3 Outcomes Research

Analyses of EQ-5D-3L, FACT-M (and GP5 item alone), and WPAI:GH scores will be performed in all randomized participants who have an assessment at baseline (Day 1, assessment prior to administration of drug on day of first dose) and at least 1 subsequent assessment while on treatment. Questionnaire completion rate, defined as the proportion of questionnaires actually received out of the expected number, will be calculated and summarized at each assessment point.

EQ-5D-3L data collected during on-study clinic visits, at Follow-up Visits 1 and 2, and during the survival follow-up phase, will be described by treatment group as randomized in the following ways:

- EQ-5D-3L index scores and post-baseline changes in scores will be summarized at each assessment time point using descriptive statistics (ie, N, mean with SD and 95% CI, median, first and third quartiles, minimum, maximum). In the base case, scores will be calculated using the UK preference-weighting algorithm.
- EQ-5D-3L VAS scores and post-baseline changes in scores will be summarized at each assessment time point using descriptive statistics (ie, N, mean with SD and 95% CI, median, first and third quartiles, minimum, maximum).
- The proportion (N) of participants reporting no, moderate, or extreme problems will be presented for each of the 5 EQ-5D-3L dimensions at each assessment time point.
- A by-participant listing of the level of problems in each dimension, corresponding EQ-5D-3L health state (ie, 5-digit vector), EQ-5D-3L index score, and EQ-5D-3L VAS score will be provided.

FACT-M data collected during on-study clinic visits, at Follow-up Visits 1 and 2, and during the survival follow-up phase will be described by treatment group as randomized in the following ways:

- Scores and post-baseline changes in scores for the FACT-M total scale and subscales, and the GP5 will be summarized at each assessment time point using descriptive statistics (ie, N, mean with SD and 95% CI, median, first and third quartiles, minimum, maximum, and frequency of responses for GP5 item).
- The proportion (N) of participants with symptomatic deterioration, defined as a clinically meaningful decline in FACT-M MS score (worsening from baseline ≥ 34 points) or death, will be summarized at each assessment time point (on-study visits only).

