**Table 3-1: Study Objectives and Endpoints**

Objectives	Endpoints
Phase 3 Primary Objective	
The Phase 3 primary objective is to compare PFS of BMS-986213 to nivolumab monotherapy in participants with previously untreated, unresectable, or metastatic melanoma.	PFS time as assessed by a Blinded Independent Central Review (BICR), using RECIST v1.1. PFS is defined as the time between the date of randomization and the first date of documented progression, or death due to any cause, whichever occurs first.
Phase 3 Secondary Objectives	
To compare OS of BMS-986213 to nivolumab monotherapy in participants with previously untreated, unresectable or metastatic melanoma.	OS is defined as the time between the date of randomization and the date of death due to any cause.
To compare ORR of BMS-986213 to nivolumab monotherapy in participants with unresectable or metastatic melanoma	ORR as assessed by a BICR. The ORR is defined as the number of subjects with a best overall response (BOR) of complete response (CR) or partial response (PR) divided by the number of randomized subjects for each treatment group. The BOR is defined as the best response designation, recorded between the date of randomization and the date of objectively documented progression per RECIST v1.1 or the date of subsequent anti-cancer therapy, whichever occurs first.
Phase 3 Tertiary/Exploratory Objective	
To evaluate duration of and time to objective response	Duration of response (DOR) is defined as the time between the date of first response to the date of first documented tumor progression (per RECIST v1.1) or death due to any cause. Time to objective response (TTR) is defined as the time from randomization to the date of the first documented CR or PR.
To evaluate PFS, ORR, DOR, and OS of BMS-986213 to nivolumab monotherapy in subgroups based on combinations of LAG-3 expression ( $\geq 1\%$ expression versus $< 1\%$ expression) and PDL-1 status ( $\geq 1\%$ tumor cell surface expression versus $< 1\%$ tumor cell surface expression) among participants with unresectable or metastatic melanoma treated with BMS-986213 compared to those treated with nivolumab monotherapy.	PFS time as assessed by a BICR using RECIST v1.1. ORR as assessed by a BICR. DOR. TTR. OS.

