To evaluate the difference in symptom burden between participants with unresectable or metastatic melanoma treated with BMS-986213 and those treated with nivolumab monotherapy.	Time to meaningful symptomatic deterioration (TTSD) as measured by the Functional Assessment of Cancer Therapy – Melanoma (FACT-M) Melanoma Subscale (MS).

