#### **4.3.4.2 FACT-M**

The FACT-M questionnaire will be used to assess the effects of disease symptoms on functioning and well-being. The FACT-M includes the 27-items from the FACT General (FACT-G) to assess physical well-being (PWB; seven items), social/family well-being (SWB; seven items), emotional well-being (EWB; six items), and functional well-being (FWB; seven items). In addition, the FACT-M includes a 16-item disease-specific melanoma subscale (MS) and an 8-item melanoma surgery scale (MSS). The GP5 item, which will also be analyzed on its own is: "I am bothered by side effects of treatment".

Each FACT-M item is rated on a 5-point scale ranging from 0 (not at all) to 4 (very much). Scores for the PWB, FWB, SWB, and EWB subscales can be combined to produce a FACT-G total score, which provides an overall indicant of generic quality of life, while the FACT-G and MS scores can be combined to produce a total score for the FACT-M, which provides a composite measure of general and targeted quality of life.

A variant of the total score that is often more sensitive to physical and functional outcomes, the Trial Outcome Index, can be derived by summing the PWB, FWB, and MS scores. All scores are scaled so that higher values indicate better functioning as well as lower symptom burden.

For any given scale, the minimally important difference represents the smallest difference in score that informed patients might perceive as important and that would warrant consideration of a change in management. With regard to the MS, the minimally important difference has been estimated as a change of 2-4 points. For this trial, we will use the midpoint of the range (i.e., a change  $\geq 3$  points) to define a minimally important change in MS score. This interpretation has been applied in previous investigations.

Data will be scored according to the algorithm described in the FACT-M scoring manual.

If there are missing items, subscale scores can be prorated. This can be done using the following formula:

$$\text{Prorated subscale score} = [\text{Sum of item scores}] \times [\text{N of items in subscale}] \div [\text{N of items answered}]$$

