### 5.2.1 Phase 3 Testing Strategy

The overall alpha for the Phase 3 study is 0.05 (two-sided).

For the Phase 3 study, type I error control across endpoints will be performed hierarchically (see [Figure 5.2.1-1](#)). The primary analysis is for PFS. If that analysis is significantly superior, then the secondary endpoints may be tested in the order of OS followed by ORR. That is, if the results comparing PFS between treatment groups are significant at the applicable alpha level, then results comparing OS between treatment groups will be interpreted. If the results comparing OS between treatment groups are significant, then results comparing ORR between treatment groups will be interpreted. Other endpoints will not be tested formally.

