### **7.9.3 Time to Meaningful Symptomatic Deterioration of FACT-M MS**

The time to meaningful symptomatic deterioration is defined as the time (in months) between the date of randomization and the first date of a 3-point or more decrease from baseline in FACT-M Melanoma Subscale (MS). The focus of this analysis is the period while patients remain on treatment; subjects who did not meet the criteria of a 3-point or more increase from baseline in FACT-M MS will be censored on the date of their last FACT-M assessment. Patients without any PRO measurement are censored at randomization.

Time to meaningful symptomatic deterioration will be analyzed using a Cox proportional hazards model with baseline as a covariate. The estimate of the hazard ratio along with a two-sided 95% CI for the hazard ratio will be calculated.

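### SAP 7.9.3 defines the FACT-M MS deterioration event as a fall of 3 points or more, but its censoring sentence refers to a rise

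*SAP*

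**What the plan says.** SAP 7.9.3 measures TTSD from randomization to "the first date of a 3-point or more decrease from baseline in FACT-M Melanoma Subscale (MS"). Later in the same section, the censoring rule is that "subjects who did not meet the criteria of a 3-point or more increase from baseline in FACT-M MS will be censored" at the date of their last FACT-M assessment. A further sentence censors patients with no patient-reported data at randomization. TTSD is then analysed with a Cox model that has the baseline score as a covariate, and the hazard ratio is reported with a 95% confidence interval.

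On the direction of the scale, SAP 4.3.4.2 states: "All scores are scaled so that higher values indicate better functioning as well as lower symptom burden". Protocol 9.1.3.2 says the same. Protocol 10.2.4.3 describes "symptomatic deterioration, defined as a clinically meaningful decline in FACT-M MS score".

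On the status of the endpoint, SAP Table 3-1 lists "Time to meaningful symptomatic deterioration (TTSD) as measured by the Functional Assessment of Cancer Therapy" under the heading "Phase 3 Tertiary/Exploratory Objective". After setting out the PFS, OS, ORR sequence, SAP 5.2.1 adds: "Other endpoints will not be tested formally".

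**The concern.** The event rule and the censoring rule together form the derivation specification for a time-to-event variable. They should be complementary: whoever does not meet the event criterion is censored. Here they use the same scale and the same 3-point threshold but opposite directions, so they are not complementary.

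What is at stake is limited but concrete. The sentence is an operative rule behind a planned hazard ratio, and SAP Section 9 puts all SAP analyses in the clinical study report unless otherwise noted. Followed to the letter, the rule cannot be programmed without a choice that the SAP does not record. That choice would now be made after subject-level unblinding, which the 04AUG2021 update in SAP 5.2.1 says has taken place.

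**Working it through.** The plan gives no figure to reproduce. The check compares the texts and then lists the possible cases.

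**Step 1: which word is wrong?**

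- Event definition, SAP 7.9.3: a decrease.
- Censoring sentence, SAP 7.9.3: an increase.
- Scale direction, SAP 4.3.4.2 and Protocol 9.1.3.2: higher is better, so worsening is a decrease.
- Protocol 10.2.4.3: symptomatic deterioration is a decline.
- Section title, SAP 7.9.3: deterioration.

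The censoring sentence is the only one that points the other way. The document history in SAP Section 10 does not correct it; version 2.1 changed Section 7.9 and left this word alone. The sentence is complete and legible, so neither redaction nor text conversion explains it.

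I use Protocol 10.2.4.3 for direction only. In the available text its threshold reads 34 points, against 3 points in Protocol 9.1.3.2 and SAP 7.9.3. That may be a misprint or a conversion artefact, and nothing here depends on it.

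**Step 2: what does the literal rule do?**

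Take participants with a baseline MS score and at least one later one. Classify each by whether the score ever falls by 3 points or more (F) and ever rises by 3 points or more (R). As written, a participant is an event if F = yes and is censored if R = no. With *decrease* in the censoring sentence, a participant is an event if F = yes and is censored if F = no.

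| F | R | As written | With *decrease* |
|---|---|---|---|
| yes | no | event and censored | event |
| no | yes | neither | censored |
| yes | yes | event | event |
| no | no | censored | censored |

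As written, 2 of the 4 patterns have no single outcome. With the one-word change, 0 of the 4 do. These are logical patterns, not participant counts. The documents do not say how many participants fall into each, so the effect on the hazard ratio cannot be calculated.

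**The case against.** The strongest reply is that nobody would be misled. The censoring sentence refers to not meeting the criteria, which points back to the criterion just defined. The scale direction is stated in both documents and the title says deterioration. A competent programmer would read *increase* as a slip. The endpoint is exploratory and carries no alpha. On that view the matter is editorial.

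Most of this stands, and it is why the point is minor. It does not remove the point: the text contradicts itself, nothing in the SAP corrects it, and a derivation rule should not rely on the programmer setting one of its sentences aside.

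A reader might also infer more than the documents support:

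- *That the reported hazard ratio is wrong or reversed.* The documents do not show how TTSD was programmed, and the event definition is in the right direction.
- *That correcting the word also settles deaths.* It does not. SAP 7.9.3 is silent on death, while Protocol 10.2.4.3 counts death in its by-visit deterioration summary. That is a proportion and not TTSD, so it does not fix the TTSD rule either way.
- *That after the correction every participant has one defined outcome.* The table covers only participants with MS scores. Under Protocol 9.1.3, participants under 18 complete EQ-5D-3L but not FACT-M. They can have patient-reported data without a FACT-M date, and the one-word change does not say how they are handled.
- *That the assessment window is part of the same error.* The section says "The focus of this analysis is the period while patients remain on treatment", yet the MS is also collected at Follow-Up Visits 1 and 2 and at survival visits (Protocol 9.1.3 and Table 2-3). How that focus is applied is a separate request for detail. It has no bearing on the direction of the change.

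**Conclusion.** The censoring sentence in SAP 7.9.3 is wrong as written: *increase* should read *decrease*. Read literally, it makes participants who only decline both events and censored, and leaves those who only improve without a censoring rule.

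Severity is minor. No alpha, power or result in the testing hierarchy depends on TTSD. The conclusion rests on the stated scale direction, on which both documents agree, and on the section's own event definition being the intended one. It assumes nothing about how often each pattern occurs.

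**What to change.** In the censoring sentence of SAP 7.9.3, replace *increase* with *decrease*. Keep the event definition, the censoring date and the rule that censors patients with no patient-reported data at randomization.

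Record the change in the document history (SAP Section 10) as a correction of wording. Because treatment assignments are already unblinded, the entry should say that the event definition has not changed.

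The cost is one word and one history entry. No new data are needed, and nothing changes in the primary or secondary analyses.

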## 2.2 Treatment Assignment

After the subject's initial eligibility is established and informed consent has been obtained, the subject must be enrolled into the study by accessing an Interactive Response Technologies web-based system (IRT) to obtain the subject number. Every subject that signs the informed consent form must be assigned a subject number in IRT. The investigator or designee will register the subject for enrollment by following the enrollment procedures established by BMS. The following information is required for enrollment:

- Date that informed consent was obtained
- Date of birth
- Sex at birth.

Once enrolled in IRT, enrolled subjects that have met all eligibility criteria will be ready to be randomized through the IRT. The following information is required for subject randomization:

- Subject number
- Date of birth
- PD-L1 Expression: PD-L1  $\geq$ 1% tumor cell surface expression vs. PD-L1 <1% tumor cell surface expression /non-quantifiable (entered at IRT)
- LAG-3 Status: LAG-3  $\geq$  1% expression/ LAG-3 <1% expression (entered at IRT)
- BRAF Status: Mutation Positive/ Mutation Wild-type at IRT
- AJCC M Stage: M0/M1any[0] / M1any[1]) at IRT

Subjects meeting all eligibility criteria will be randomized in a 1:1 ratio to BMS-986213 or Nivolumab monotherapy and stratified by PD-L1 expression level (PD-L1  $\geq$ 1% expression vs PD-L1 < 1% expression), LAG-3 expression (LAG-3  $\geq$  1% expression vs LAG-3 < 1% expression), BRAF (Mutation Positive/ Mutation Wild-type ) and M stage (M0/M1any[0] / M1any[1]). The randomization procedures will be carried out via permuted blocks within each stratum.

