### **7.5 Efficacy**

Below is a brief summary table (Table 7.5-1) of planned statistical analyses of the primary and secondary efficacy endpoints. Following the summary table are more details about each analysis in individual sections.

Unless stated otherwise, whenever a stratified analysis is specified, the following stratification factors will be used PD-L1, LAG-3, BRAF, AJCC M Stage. Each of the 4 stratification factors has 2 levels, with 16 strata in total. Anticipating the study population may not be equally distributed across levels in a given stratification factor, it is likely that the number of subjects in some strata may be small. With 2 treatment arms in this study, the stratum size with less than 10 subjects would likely cause unreliable estimates in the stratified analyses Therefore, in the case of less than 10 subjects in a strata or in the case of unexpected model convergence issues due to small strata with too small event numbers, stratification factors would be removed one at a time from the model until convergence is achieved. This will happen in the following order: (1) PD-L1 and (2) the stratification factor with the lowest prevalence in a level. A sensitivity analysis of PFS will be performed using the original stratification variables as per IRT.

- PD-L1 Expression: PD-L1 $\geq$ 1% tumor cell surface expression vs PD-L1 $<$ 1% tumor cell surface expression/ non-quantifiable (from LabCorp LA)
- LAG-3 Status: LAG-3 $\geq$ 1% expression vs LAG-3 $<$ 1% expression (from IRT)
- BRAF Status: Mutation Positive/ vs Mutation Wild-type (from IRT)
- AJCC M Stage: M0/M1any[0] vs M1any[1] (from lab value and eCRF)

All p-values reported will be two-sided.

CI's for the efficacy endpoints will be at the two-sided 95% level. The p-values presented in the CSR will be rounded to the fourth decimal place. Point estimates and confidence bounds for efficacy variables will be rounded to the second decimal place.

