### 7.5.1 Analysis of Progression-Free Survival

The primary objective of the study is to compare the progression-free survival (as determined by BICR) between treatment groups in all randomized subjects.

The analysis of PFS (as determined by BICR) will be to compare the two treatment groups via a stratified log-rank test among all randomized subjects. The primary definition of PFS adjusting for subsequent anticancer therapy will be used in this analysis. The two-sided log-rank p-value will be reported. The estimate of the PFS hazard ratio between treatment groups will be calculated

using a stratified Cox proportional hazards model. Ties will be handled using the exact method. A two-sided 95% CI for the hazard ratio will also be presented.

The PFS function for each treatment group will be estimated using the KM product limit method and will be displayed graphically. A two-sided 95% CI for median PFS in each treatment group will be computed via the log-log transformation method. PFS rates at fixed time points (e.g., 6 months, depending on the minimum follow-up) will be presented along with their associated 95% CIs. These estimates will be derived from the Kaplan Meier estimate and corresponding CIs will be derived based on Greenwood formula for variance derivation and on log-log transformation applied on the survivor function.

The source of PFS event (progression or death) will be summarized by treatment group.

The status of subjects who are censored (as per primary definition of PFS) in the PFS KM analysis will be tabulated for each randomized treatment group including the following categories:

- On-study (on-treatment, in follow-up)
- Off-study (lost to follow-up, withdraw consent, never treated)
- No baseline tumor assessment
- No on-study tumor assessment and no death
- Received subsequent anticancer therapy

PFS will also be reported as per investigator.

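### The Cox model for time to symptomatic deterioration (SAP 7.9.3) omits the four randomization factors; the effect is small and conservative, and the change is cheap but now comes after unblinding

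*SAP*

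**What the plan says.** SAP 7.9.3 gives the model in one sentence: "Time to meaningful symptomatic deterioration will be analyzed using a Cox proportional hazards model with baseline as a covariate". The output is an estimate only: "The estimate of the hazard ratio along with a two-sided 95% CI for the hazard ratio will be calculated". No strata, p-value or alpha is mentioned, and baseline is not identified, although the baseline MS score is presumably meant.

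The general rule in SAP 7.5 is conditional: "Unless stated otherwise, whenever a stratified analysis is specified, the following stratification factors will be used PD-L1, LAG-3, BRAF, AJCC M Stage". Section 7.9.3 specifies no stratified analysis, so the rule does not reach it.

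The factors are part of the design. SAP 2.2 says: "The randomization procedures will be carried out via permuted blocks within each stratum". The PFS hazard ratio is estimated (SAP 7.5.1) "using a stratified Cox proportional hazards model. Ties will be handled using the exact method", and OS is compared by a stratified log-rank test with a stratified hazard ratio (SAP 7.5.4). The multivariate PFS model in SAP 7.5.2 adds baseline covariates and keeps the randomization factors as strata.

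Time to symptomatic deterioration is a Phase 3 tertiary/exploratory endpoint (SAP Table 3-1), with the objective of evaluating the between-arm difference in symptom burden. SAP 5.2.1 limits formal testing to PFS, OS and ORR. The other patient-reported analyses (SAP 7.9.1, 7.9.2 and 7.9.4) are descriptive.

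**The concern.** An analysis should normally reflect the factors by which participants were randomized. If those factors predict the outcome and are left out of a Cox model, the hazard ratio is pulled towards 1. Blocked randomization within strata also makes the usual standard error somewhat too large for the unstratified estimate, so the inference is conservative.

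The closest precedent in the SAP is the covariate-adjusted PFS model, which adds baseline covariates and retains the strata. Section 7.9.3 also adds a baseline covariate but drops the strata, without giving a reason. At stake is a modest loss of precision in the only comparative symptom estimate, and a hazard ratio that is marginal over the four factors while the main PFS and OS hazard ratios are conditional on them.

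**Working it through.** **What can be reproduced.** The documents give no event count, effect size, power or alpha for this endpoint, so there is no planned figure to reproduce. The size of the effect has to be illustrated under assumptions.

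**Inputs from the documents.** About 700 participants randomized 1:1 (SAP 5.2); four two-level factors, hence 16 strata (SAP 7.5); permuted blocks within strata (SAP 2.2).

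**Assumptions.** Within-stratum hazard ratio 0.75, or 1.0 under the null; exponential times; 30% or 50% of participants with an event; blocks of 4; each factor at 50% prevalence; the same prognostic hazard ratio for each factor (1.0, 1.25, 1.5 or 2.0); 1,000 replicates per row. Baseline MS score is not simulated.

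**Check of the simulation.** With non-prognostic factors, power should match Φ(√(d/4) × |ln 0.75| − 1.96), where |ln 0.75| = 0.2877.
- d = 0.30 × 700 = 210: √52.5 × 0.2877 − 1.96 = 0.125, so 55.0%. The simulation gave 54.3%.
- d = 0.50 × 700 = 350: √87.5 × 0.2877 − 1.96 = 0.731, so 76.8%. The simulation gave 76.4%.

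**Results** (U = unstratified Cox, S = Cox stratified on all 16 strata; rejection at two-sided 5%).

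| HR per factor | Events | Mean HR, U | Mean HR, S | Power, U | Power, S | Null rejection, U | Null rejection, S |
|---|---|---|---|---|---|---|---|
| 1.0 | 30% | 0.749 | 0.750 | 54.3% | 53.4% | 4.0% | 4.0% |
| 1.0 | 50% | 0.752 | 0.753 | 76.4% | 75.4% | 3.9% | 4.0% |
| 1.25 | 30% | 0.753 | 0.751 | 53.1% | 53.8% | 5.3% | 5.6% |
| 1.25 | 50% | 0.754 | 0.751 | 74.2% | 75.4% | 3.6% | 4.0% |
| 1.5 | 30% | 0.760 | 0.753 | 52.1% | 54.1% | 2.9% | 3.6% |
| 1.5 | 50% | 0.763 | 0.752 | 72.5% | 75.6% | 4.5% | 4.5% |
| 2.0 | 30% | 0.767 | 0.749 | 48.5% | 55.6% | 3.6% | 5.1% |
| 2.0 | 50% | 0.782 | 0.752 | 64.5% | 75.0% | 2.4% | 5.0% |

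**Reading the table.**
- Up to a factor hazard ratio of 1.5, the largest shift is 0.763 − 0.752 = 0.011 and the largest power difference is 75.6 − 72.5 = 3.1 points. With no prognostic value, stratifying costs about 1 point.
- At 2.0 the shifts are 0.767 − 0.749 = 0.018 and 0.782 − 0.752 = 0.030, and the power differences are 7.1 and 10.5 points. This case is extreme: the worst stratum has 2.0⁴ = 16 times the hazard of the best, against 1.5⁴ = 5.1 times at 1.5.
- Unstratified null rejection runs from 2.4% to 5.3%. The Monte Carlo standard error at 5% is √(0.05 × 0.95/1000) = 0.7 points, so there is no sign of inflation, and the lowest values point to conservatism.

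**Shift against sampling error.** Taking SE(log HR) ≈ 2/√d, the 95% CI around 0.75 runs from 0.57 to 0.98 with 210 events and from 0.61 to 0.92 with 350. A shift of 0.01 to 0.03 is small beside either.

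**Sparse strata.** Equal strata would hold 700/16 = 44 participants. With assumed prevalences of 0.40, 0.75, 0.40 and 0.35, the smallest expected stratum is 700 × 0.40 × 0.25 × 0.40 × 0.35 = 9.8, just under the threshold of 10 in SAP 7.5.

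**The case against.** The strongest case for leaving the model alone has five parts.

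1. **Similar analyses are also unstratified.** A reader might infer that the trial stratifies all its other time-to-event comparisons. The documents do not support that. OS subset hazard ratios are unstratified (SAP 7.5.5). SAP 7.5.2 includes an unstratified log-rank test and an unstratified Cox model for PFS, though that Cox model carries the four factors as covariates. The exploratory biomarker Cox models (SAP 7.8.5.2) specify no strata and do not name BRAF or M stage. PFS2, DOR and treatment-free interval have no stratified comparison specified. This stands: the contrast holds for the main PFS and OS comparisons and the covariate-adjusted PFS model.

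2. **No test is planned.** This stands. The power figures are only a way of expressing precision, and a conservative bias cannot produce a false claim of benefit.

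3. **Prognostic strength is assumed.** Protocol 5.4.3 links the factors to prognosis and treatment response, not to decline in the MS score. The planned baseline covariate may also absorb some of the variation between strata. This stands and argues for the lower end of the range.

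4. **Stratifying would not make the hazard ratio fully comparable with those for PFS and OS.** This also stands: the event differs and the model conditions on baseline score. Stratifying removes one source of difference.

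5. **The change is not free.** SAP 7.5 warns that "the stratum size with less than 10 subjects would likely cause unreliable estimates in the stratified analyses", and the sponsor is already unblinded at subject level (SAP 5.2.1). Both stand as costs. Neither is prohibitive, since SAP 7.5 already has a rule for sparse strata and both models can be reported.

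**Conclusion.** The point holds as a low-cost improvement. As written, the Cox model for symptomatic deterioration omits the four randomization factors, and no general rule brings them in. The illustrated cost is an attenuation of about 0.00 to 0.03 on a hazard ratio of 0.75. The precision loss is worth about 0 to 3 points of power for factor hazard ratios up to 1.5, and about 7 to 10 points only if every factor has a hazard ratio of 2.0. These figures rest on assumed event fractions, prevalences and prognostic strengths, and on a simulation without the baseline score.

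A reader might go further and infer inflated type I error or a threat to the trial's formal conclusions. Neither follows: the direction is conservative, and the endpoint lies outside the PFS, OS and ORR hierarchy.

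**What to change.** Revise SAP 7.9.3 to specify a Cox model stratified by PD-L1, LAG-3, BRAF and M stage, using the data sources and small-stratum rule of SAP 7.5, with baseline MS score as a covariate. Keep the hazard ratio and two-sided 95% CI as the output.

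The cost is small:
- The strata are already derived for PFS and OS.
- Sparse strata may require dropping factors under the SAP 7.5 rule, PD-L1 first. FACT-M is completed only by participants aged 18 or over at baseline (Protocol 9.1.3), so the factors retained could differ from those used for PFS. The report should state which were retained.
- The primary analysis of 09 March 2021 led to subject-level unblinding, and the current SAP is dated 25 October 2021. Date the change, record it as post-unblinding, and report the currently specified unstratified model beside the stratified one.

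The same revision should reconcile the endpoint definition. SAP 7.9.3 defines the event as a 3-point decrease but words the censoring rule in terms of a 3-point increase. Protocol 10.2.4.3 gives a threshold of 34 points, or death, for the related proportion summary, against 3 points in Protocol 9.1.3.2. These are separate from stratification and matter more to what is being estimated.
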